## 10.0 STATISTICAL METHODS

### 10.1 Statistical Plan

A Statistical Analysis Plan (SAP), detailing the intended statistical analysis of the study data, will be prepared as a separate document and finalized prior to database lock. Any deviation from the original statistical plan will be described and justified in the final report, as appropriate. The procedure for accounting for missing, unused and spurious data will be included in the Statistical Analysis Plan.

All statistical analysis will be conducted using SAS®, Version 9.4 or higher.

#### 10.1.1 Determination of Sample Size

The sample size of 35 patients, stratified by age and % BSA, was determined to be sufficient.

#### 10.1.2 Baseline Comparability

Baseline comparability of the two groups will be assessed using appropriate statistical tests (e.g., one-way analysis of variance, Fisher's exact test, Cochran-Mantel-Haenszel test). The groups will be compared for basic demographics (age, gender, ethnicity and race), baseline IGA, baseline EASI score and baseline total BSA. Summary tables by group will be presented.

#### 10.1.3 Safety Analysis of Potential HPA Axis Suppression

Dosing will be twice a day for 28 days excluding the doses prior to the Cortisol Response Test (54 applications). All patients who are enrolled, use at least 42 doses of the study drug and have data

## **CONFIDENTIAL PROTOCOL**

An Open Label, Safety Study to Assess the Potential for Adrenal Suppression Following Treatment with Desoximetasone 0.15% Topical Spray (Taro Pharmaceuticals U.S.A., Inc.) in Patients with Atopic Dermatitis

---

from a post-treatment cortisol response test will be included in the analysis. Patients who have not used 42 doses of the study drug will be excluded from the primary analysis of HPA axis suppression.

The primary analysis of interest is the proportion of patients in each group who are considered to have demonstrated possible HPA axis suppression following treatment with the study medication. As a secondary analysis of the data a logistic regression of the proportion of patients in the study with HPA axis suppression will be performed with %BSA affected as a covariate. See Appendix E for results from the cortisol response test considered indicative of potential HPA axis suppression.

The study will be enrolled by Cohort starting with Cohort 1 and each cohort will be reviewed for the potential of HPA axis suppression. If at least 50% of patients in Cohort 1 experience HPA axis suppression once the minimum number of patients has been enrolled and completed the cohort, enrollment for that cohort will be stopped and no further cohorts will be initiated. If at least 35% of patients have experienced HPA axis suppression across cohorts combined during the study, enrollment will be discontinued and no other cohorts will be initiated. Cohort 2 will not begin until safety data has been reviewed for Cohort 1. The same process will be followed for each Cohort until the study is complete.

For all patients the actual amount of desoximetasone (mg) applied during the study will be calculated from recorded bottle weights and presented.

### **10.2 Safety Analysis**

Safety analysis will be conducted on all patients who applied at least one dose of study drug.

Adverse medical events experienced by the patients will be tabulated. The relationship of AEs, if any, to the study drug will be assessed by the Investigator. Adverse events assessed as definite, probable, possible or not related to the study drug will be presented. Shift analysis using the categories, below, above and within the laboratory normal range will be performed to identify any specific laboratory parameter that shows a trend toward potentially clinically significant changes.

## **11.0 REGULATORY OBLIGATIONS**

### **11.1 Institutional Review Board**

The study protocol, informed consent/assent form, Investigator's Brochure, or package insert (as applicable), and any specific advertising will be submitted to, and approved by, an Institutional Review Board (IRB) before the start of the study. A form must be signed by the chairman or designee of the IRB noting the approvals. This notification of the board's approval along with a description by profession and gender of the board's composition will be provided to the Sponsor.

### **11.2 Study Documentation**

This study will be conducted in compliance with the protocol, Good Clinical Practices (GCPs) and all applicable regulations, including the Federal Food, Drug and Cosmetics Act, US applicable Code of Federal Regulations (title 21), parts 50, 56, 312, 320 and any IRB requirements relative to clinical

## **CONFIDENTIAL PROTOCOL**

An Open Label, Safety Study to Assess the Potential for Adrenal Suppression Following Treatment with Desoximetasone 0.15% Topical Spray (Taro Pharmaceuticals U.S.A., Inc.) in Patients with Atopic Dermatitis

---

studies and the Declaration of Helsinki, June 1964, as modified by the 59th World Medical Association General Assembly, October 2013.

The Investigator will permit trial-related monitoring, audits, IRB review and regulatory inspections providing direct access to source data/documents.

### **11.2.1 Protocol**

The Investigator indicated on FDA Form 1572 will act as the Principal Investigator at each study site. Protocols will be noted as approved by placement of the Novum Representative's signature on the cover page. The Sponsor of the study will also approve the protocol by having a study-responsible individual sign the protocol cover page.

### **11.2.2 Informed Consent**

An Informed Consent Form (ICF) that includes all of the relevant elements currently required by FDA and local State regulations will be provided to each prospective study patient's parent/legal guardian before enrollment into the study. In addition, subjects 11-17 years of age will be presented with an Assent Form. The type and method of study, tests to be administered, any potential or possible hazards, and the patient's right to withdraw from the study at any time will be explained to the patients by the Investigator or designee. Once the Investigator or designee is assured that an individual candidate understands the implications of participating in this study, the parent/legal guardian will be asked to give consent by signing and dating the ICF/Assent Form and the patient will be asked to give assent by signing and dating in the appropriate areas of the Assent. The Investigator or designee will also sign and date the form, along with a staff member who will sign the ICF as a witness to verify that the patient has indeed received information. For illiterate patients, verbal consent should be obtained in the presence of and be countersigned by a literate witness. If any other language is required, translation will be performed by a certified translator. A copy of the ICF will be provided to the patient.

### **11.2.3 Protocol and Informed Consent Changes**

Revisions to the original protocol will be documented in amendments, incorporated as a preface to the new version and approved by the IRB. Any revision that substantially alters the study design or increases potential risk to the patient requires the patient's consent to continue in the study. Revisions to the original ICF will also be approved by the IRB. The approvals will be processed in accordance with the established IRB procedures. Copies of all protocol and ICF amendments/revisions, along with letters noting IRB approval, will be submitted to the Sponsor.

### **11.2.4 Source Documents and Case Report Forms**

All patients will be identified by initials, date of birth, and a unique patient number. Source documents will be used to record all study-related data. Source document entries will be used to complete Case Report Forms (CRFs). A set of CRFs will be completed for each patient enrolled in the study. All data and CRFs will be reviewed, evaluated and signed by the Investigator, as required.

The original source documents and a copy of the corresponding CRFs will be retained by the Investigator. Patients who terminate early from the study will have the end of study (Visit 3) source/CRF completed.

## **CONFIDENTIAL PROTOCOL**

An Open Label, Safety Study to Assess the Potential for Adrenal Suppression Following Treatment with Desoximetasone 0.15% Topical Spray (Taro Pharmaceuticals U.S.A., Inc.) in Patients with Atopic Dermatitis

---

### **11.2.5 Drug Accountability**

All drug receipt, inventory, dispensing, dosing and reconciliation records will be maintained in compliance with Federal Regulations. The study drug will be dispensed to qualified study patients according to established procedures. At the end of the study (after the database has been locked) all used and unused study drug will be returned to Novum.

### **11.2.6 Drug Storage**

All study drug will be stored at controlled room temperature 15-30°C (59-86°F), in a secure place with access by authorized individuals only. The Investigator will be responsible for maintaining accurate records of drug receipt, dispensing, and return. At the end of the study, all partially used and unused study drug will be returned to Novum.

### **11.2.7 Pregnancies**

Patients with a positive pregnancy test during screening will not be enrolled in the study. Patients who report that they have become pregnant during the study or have a positive pregnancy test at any clinic visit will be followed to completion of the pregnancy. The pregnancy will be reported as an AE.

Female patients of childbearing potential must have been using and must agree to continue to use accepted methods of birth control, throughout the study. All female patients are considered to be of childbearing potential unless they are premenarchal, have been surgically sterilized or have been postmenopausal for at least 1 year. Abstinence is an accepted method of birth control. Alternatively, any of the following methods of birth control are acceptable: oral contraceptives, contraceptive patches/implants (e.g., Norplant®), Depo-Provera®, double barrier methods (e.g., condom and spermicide) or IUD. Prior to study enrollment women of child bearing potential must be advised of the importance of avoiding pregnancy during study participation.

A negative result of a urine pregnancy test having a minimum sensitivity of at least 25 mIU/ml for hCG should be obtained, prior to study participation. Pregnancy testing will be performed at Visits 1, 2 and 3 and the results of all pregnancy tests (positive or negative) will be documented.

If following initiation of study treatment, it is subsequently discovered that a study patient is pregnant or may have been pregnant at the time of Investigational Product exposure, the Investigational Product will be permanently discontinued. The Principal Investigator must immediately notify the Medical Monitor of this event.

Protocol-required procedures for study discontinuation and follow-up must be performed on the patient. Other appropriate pregnancy follow-up procedures should be considered if indicated. In addition, the Principal Investigator must report to the sponsor follow-up information regarding the course of the pregnancy, including perinatal and neonatal outcome. Infants should be followed for a minimum of eight weeks after birth.

### **11.2.8 Reporting Safety Information to the IRB**

The Investigator must promptly report to the Investigator's IRB all unanticipated problems involving risks to patients. This includes death from any cause and all serious adverse events occurring during the study, regardless of the assessed causality.

## **CONFIDENTIAL PROTOCOL**

An Open Label, Safety Study to Assess the Potential for Adrenal Suppression Following Treatment with Desoximetasone 0.15% Topical Spray (Taro Pharmaceuticals U.S.A., Inc.) in Patients with Atopic Dermatitis

---

### **11.2.9 Record Retention**

All drug accountability records, CRFs, source data and related regulatory documents must be retained for at least ten years following completion of the study or for two years after the test product has been approved for marketing by the Food and Drug Administration.

### **11.2.10 Study Monitoring and Auditing**

Novum will be responsible for monitoring the study according to Good Clinical Practice and applicable regulations. Monitoring visits are for the purpose of confirming adherence to the protocol and to verify complete and accurate data collection. The clinical site will make all records associated with the study available to Novum's representative during such visits and audits

The study may be subject to audit by the Sponsor, Sponsor Representative or by regulatory authorities. If such an audit occurs the Investigator must agree to allow access to required patient records. By signing this protocol, the Investigator grants permission to personnel from the Sponsor, its representatives and appropriate regulatory authorities for on-site monitoring of all appropriate study documentation, as well as on-site review of study procedures.

### **11.2.11 End of the Trial**

The end of the trial is defined as the time at which the last patient has completed their last visit in the study. Upon completion of the study, the study drug will no longer be available to the patient but the Investigator can, at their discretion, discuss alternative treatments with the patient.

### **11.2.12 Clinical Study Report**

At the end of the study a full report in e-CTD format will be prepared that will include a narrative of the clinical conduct and results of the study, a statistical report including a description of the analysis performed, and other documentation as may be appropriate.

## CONFIDENTIAL PROTOCOL

An Open Label, Safety Study to Assess the Potential for Adrenal Suppression Following Treatment with Desoximetasone 0.15% Topical Spray (Taro Pharmaceuticals U.S.A., Inc.) in Patients with Atopic Dermatitis

## CONFIDENTIAL PROTOCOL

An Open Label, Safety Study to Assess the Potential for Adrenal Suppression Following Treatment with Desoximetasone 0.15% Topical Spray (Taro Pharmaceuticals U.S.A., Inc.) in Patients with Atopic Dermatitis

## 13.0 APPENDICES

### APPENDIX A: Body Surface Area Calculation

#### Total Body Surface Area Calculation

To calculate the Total BSA the following procedure (Mosteller Formula) should be followed.

Total Body Surface Area (BSA) in meters squared

$$m^2 = ((\text{height (cm)} \times \text{weight (kg)}) / 3600)^{1/2}$$

**It is preferable that the patient's height and weight be measured in cm and kg however if needed:**

**To convert inches (in) to centimeters (cm) the following conversion should be used**

$$1 \text{ inch} = 2.54 \text{ cm}$$

**To convert pounds (lbs) to kilograms (kg) the following conversion should be used**

$$1 \text{ lb} = 0.45 \text{ kg}$$

The patient's height and weight should be reported to the nearest cm and nearest 0.5 kg. The BSA should be reported to the nearest second decimal place.

For example a patient who is 68 inches tall and weighs 180 lbs will have a reported BSA of:

$$68 \text{ in} \times 2.54 = 173 \text{ cm}$$

$$180 \text{ lb} \times 0.45 = 81.0 \text{ kg}$$

$$\begin{aligned} \text{BSA} &= \text{SQRT} ((173 \times 81.0) / 3600) \\ &= 1.97 \text{ m}^2 \end{aligned}$$

#### %BSA Affected

To estimate the % BSA Affected, the Investigator should use the method of approximation:

[figure not shown]
The “Rule of Nines” provides a general estimation of total BSA for several anatomic areas (each arm = 9%, each leg = 18%, back = 18%, chest and abdomen = 18%, head = 9%, groin = 1%). The Investigator may then visually estimate the proportion of the involved skin within each anatomic area and calculate the total percentage of BSA affected. In children, hips and legs are smaller and the head, neck and shoulders are larger, as a result, a modified “Rule of Nines” is used (see diagram below).

- 9% is taken from the legs and added to the head of a child < 1-year-old. For each subsequent year, 1% is returned to the legs until 9 years old at which time the head is in proportion to the adult
- By 9 years of age, the relative proportions assume the values for adult BSA and hence the adult diagram can be used as a reference at that time

**CONFIDENTIAL PROTOCOL**

An Open Label, Safety Study to Assess the Potential for Adrenal Suppression Following Treatment with Desoximetasone 0.15% Topical Spray (Taro Pharmaceuticals U.S.A., Inc.) in Patients with Atopic Dermatitis

Part	1-4 year child body % of total	5-9 year child body % of total	10-14 year child body % of total	15 year-adult body % of total
Arm	9.5%	9.5%	9.5%	9%
Head	19%	15%	12%	9%
Neck			1%	1%
Leg	15%	17%	18%	18%
Anterior trunk	16%	16%	16%	18%
Posterior trunk	16%	16%	16%	18%

**CONFIDENTIAL PROTOCOL**

An Open Label, Safety Study to Assess the Potential for Adrenal Suppression Following Treatment with Desoximetasone 0.15% Topical Spray (Taro Pharmaceuticals U.S.A., Inc.) in Patients with Atopic Dermatitis

---

**APPENDIX B: Eczema Area and Severity Index Score (EASI)**

The EASI is a composite score based on the severity of four different signs of atopic dermatitis in four different areas of the body multiplied by the percent of that specific body area affected multiplied by a weighting factor.

**Erythema**

0 = Clear	No evidence of erythema
1 = Mild	Definite light red coloration
2 = Moderate	Moderate redness, but not dark
3 = Severe	Dark red coloration

**Induration/papulation/edema**

0 = Clear	No evidence of any induration/papulation/edema
1 = Mild	Barely perceptible elevation
2 = Moderate	Clearly perceptible elevation
3 = Severe	Marked and extensive elevation

**Lichenification**

0 = Clear	No evidence of lichenification
1 = Mild	Slight thickening of skin discernible only by touch and with skin markings minimally exaggerated
2 = Moderate	Definite thickening of skin with skin marking exaggerated so that they form a visible criss-cross or ridged pattern
3 = Severe	Thickened skin with skin markings visibly portraying an exaggerated criss-cross or ridged pattern

**Excoriation**

0 = Clear	No evidence of excoriation
1 = Mild	Scant evidence of excoriation with no signs of deeper skin damage (absence of erosion or crusts)
2 = Moderate	Several linear marks of skin with some showing evidence of deeper skin injury (erosion, crust visible)
3 = Severe	Many erosive or crusty lesions present

The patient will be required to rate the severity of their pruritis (itching/scratching/discomfort) over the

## **CONFIDENTIAL PROTOCOL**

An Open Label, Safety Study to Assess the Potential for Adrenal Suppression Following Treatment with Desoximetasone 0.15% Topical Spray (Taro Pharmaceuticals U.S.A., Inc.) in Patients with Atopic Dermatitis

---

previous 24 hours using the following scale:

### **Pruritis**

0 = None	None
1 = Mild	Occasional slight itching or scratching
2 = Moderate	Constant or intermittent itching/scratching/discomfort which is not disturbing sleep
3 = Severe	Bothersome itching/scratching/discomfort which is disturbing sleep

Eczema, induration, excoriation and lichenification are part of the EASI score but pruritis is not.

### EASI Score

The EASI score is calculated as follows:

Head/neck (E + I + X + L) x Area x 0.1 (in children ages 0-7, x 0.2)

Upper Limbs (E + I + X + L) x Area x 0.2

Trunk (E + I + X + L) x Area x 0.3

Lower Limbs (E + I + X + L) x Area x 0.4 (in children ages 0-7, x 0.3)

EASI SCORE = SUM OF ABOVE 4 REGIONS

E: Erythema,

I: Induration/papulation/edema

X: Excoriation

L: Lichenification

Severity is based on the Investigator's assessment of individual signs and symptoms

0 = none, 1 = mild, 2 = moderate, 3 = severe using the definitions above

The % of each body region affected is scored as the variable Area above in the EASI formula. For the 4 body regions (head/neck, upper limbs, trunk and lower limbs) if the:

Area = 0	if % affected is 0%
Area = 1	if % affected is 1 to 9%
Area = 2	if % affected is 10 to 29%
Area = 3	if % affected is 30 to 49%
Area = 4	if % affected is 50 to 69%
Area = 5	if % affected is 70 to 89%
Area = 6	if % affected is 90 to 100%

EASI Score can be presented to the nearest whole number (no decimals and all numbers should be rounded, 0.5 should be rounded up to the nearest whole number)

**CONFIDENTIAL PROTOCOL**

An Open Label, Safety Study to Assess the Potential for Adrenal Suppression Following Treatment with Desoximetasone 0.15% Topical Spray (Taro Pharmaceuticals U.S.A., Inc.) in Patients with Atopic Dermatitis

---

The minimum score would be 0 and the Maximum Score would be 72. To be eligible for participation in this study a patient must have an EASI of at least 15 at baseline.

**CONFIDENTIAL PROTOCOL**

An Open Label, Safety Study to Assess the Potential for Adrenal Suppression Following Treatment with Desoximetasone 0.15% Topical Spray (Taro Pharmaceuticals U.S.A., Inc.) in Patients with Atopic Dermatitis

---

**APPENDIX C: Investigator Global Assessment (IGA)**

To be eligible for inclusion in the study the IGA must be 3 or 4 at baseline. To be considered a Clinical Success the patient must score a 0, 1 at Visit 3.

0	Clear	Minor, residual discoloration, no erythema or induration/papulation, no oozing/crusting
1	Almost Clear	Just perceptible erythema, with almost no induration/papulation and no oozing/crusting
2	Mild Disease	Definite pink erythema with mild induration/papulation and no oozing/crusting
3	Moderate Disease	Red erythema with moderate induration/papulation and there may be some oozing/crusting
4	Severe Disease	Dark/bright red erythema with severe induration/papulation with oozing/crusting

## **CONFIDENTIAL PROTOCOL**

An Open Label, Safety Study to Assess the Potential for Adrenal Suppression Following Treatment with  
Desoximetasone 0.15% Topical Spray (Taro Pharmaceuticals U.S.A., Inc.) in Patients with Atopic Dermatitis

---

### **APPENDIX D: Application Site Reactions**

The following application site reactions will be evaluated at each visit based on the scale provided below:

Burning

Erosion

Edema

Pain

Itching

Dryness

Absent	0	
Mild	1	(slight, barely perceptible)
Moderate	2	(distinct presence)
Severe	3	(marked, intense)

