### 7.4 Risks and Benefits

Known adverse reactions to topical corticosteroids include burning, itching, irritation, dryness, folliculitis, hypertrichosis, acneiform eruptions, hypopigmentation, perioral dermatitis, allergic contact dermatitis, maceration of the skin, secondary infection, skin atrophy, striae and milia. Dosing for extended periods of time may result in suppression of adrenal function.

CortrosynTM for injection is intended diagnostic and not therapeutic use and adverse reactions other than a rare hypersensitivity reaction are not anticipated. Known reactions are slight whealing with erythema at the site of injection.

The subject may benefit from clearing of the lesions and improvement of the condition of the disease. If the drug is approved, then many children may benefit from its use.

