### **9.4 Treatments**

#### **9.4.1 Treatments Administration**

The patient or parent/legal guardian will be instructed to apply and rub in gently a thin film of the study drug to the affected areas twice daily (morning and evening) for 28 days. The hands should be washed after applying the drug.

To ensure compliance with the dosing technique, the patient or parent/legal guardian will be instructed to apply the first dose of medication under staff supervision at the time of enrollment and then twice daily until the patient's next scheduled visit. Patient or parents/legal guardians will be instructed not to apply the study drug within 12 hours of the visit which includes the Cortisol Response Test. The patient or parent/legal guardian will be instructed not to apply the medication to the face, axilla or groin and not to use occlusive dressings on the treatment area. Each patient or parent/legal guardian will be provided with a dosing diary in which they will be required to record dosing dates and times. These diaries should be brought to each visit in order that the study staff may check compliance. At the end of the study, the dosing diaries will be retained in the patient's file as source documentation.

At Visit 1 (Screening/Enrollment) and Visit 2 (Interim Visit) qualified study patients or parents/legal guardians will be provided with one 100 ml bottle of desoximetasone 0.15% topical spray along with instructions for dosing. This bottle should be weighed before dispensing and the weight recorded. At Visit 2 (Interim Visit), the bottle should be collected, weighed and the weight recorded. A new 100 ml bottle of desoximetasone 0.15% topical spray should be weighed and the weight recorded before dispensing the spray bottle along with dosing instructions to the patient or parent/legal guardian. This bottle should be weighed and the weight recorded upon return at Visit 3 (End of Study/End of Treatment).

Treatment compliance will be encouraged by instructing the patient or parent/legal guardian on the proper dosing technique and by the use of the daily diary. Compliance will be assessed by evaluation of the diary.

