### 9.5 Study Conduct

The cortisol response test is to be done in the morning as the body's peak cortisol level is directly related to the event of awakening. **Visit 1 and Visit 3 should be scheduled before noon and subjects should not apply the study drug within 12 hours of Visit 3.**

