#### 9.5.1 Visit 1 (Day 1): Screening/Enrollment, Before 12 pm

1. **Informed Consent:** For patients under the age of majority in the state the study is being conducted (18 years in most states) the parent or legal guardian should sign the consent form and the child (age  $\geq$  11 years old) will be required to sign a patient "assent" form that will be written in such a way as to be understandable to a child. Patients age 6-10 years of age will provide verbal assent to participate.
2. **Medical History and Demographics:** The patient's demographic and a complete medical history will be obtained for the patient's current and past medical conditions.
3. **Physical Examination and % BSA Assessment:** A general physical exam will be conducted. The patient's body weight (kg) and height (cm) will also be measured while the patient is lightly clothed (e.g., no coat or shoes). %BSA will be assessed using instructions in Appendix A.
4. **Vital Signs:** The patient's vital signs will be taken and recorded (pulse, blood pressure, temperature and respiration rate).
5. **Pregnancy Test:** A urine pregnancy test will be required of all females of child bearing potential prior to enrollment.
6. **Dermatological Assessment:** Clinical signs and symptoms of AD will be evaluated by the Investigator based on the following:
  - EASI Score (Appendix B)
  - IGA Score (Appendix C)
  - Application Site Reactions (Appendix D)
7. **Concomitant Medication:** Review with the patient and parent/legal guardian the patient's use of concomitant medication within the last 12 weeks.
8. **Confirm Inclusion/Exclusion Met:** Confirm the patient meets all inclusion/exclusion criteria pending results of the Cortisol Response Test.

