## CONFIDENTIAL PROTOCOL

An Open Label, Safety Study to Assess the Potential for Adrenal Suppression Following Treatment with Desoximetasone 0.15% Topical Spray (Taro Pharmaceuticals U.S.A., Inc.) in Patients with Atopic Dermatitis

---

9. **Laboratory Evaluations:** A blood sample will be collected for hematology and clinical chemistry testing. (See Appendix G).
10. **Cortisol Response Test:** All patients will have a cortisol response test performed according to the procedure detailed in Appendix E.
11. **Dispense Study drug:** If patient is eligible to enroll, record the weight of one bottle of study drug and dispense with instructions.
12. **Apply Study Medication:** The first dose of study medication should be administered by the patient ( $\geq 12$  years of age) or parent/legal guardian at the site, under staff supervision.
13. **Provide Dosing Diary:** Provide Diary and instruct parent/legal guardian regarding how it is to be filled out and how study drug is to be used.
14. **Dispense Sunscreen:** For use only when sun exposure cannot be avoided.
15. **Provide Patient Wristband:** Each patient will receive a wristband to indicate that the patient is using a medication that has the potential to cause HPA axis suppression.
16. Schedule Visit 2.

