7.3.7 Application Site Reaction

A frequency summary table comparing application site reaction for each cohort will be presented by visit.

All data will be listed by cohort and patient.

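### Application site reactions are summarised only as frequencies by cohort and visit, so falling rates on the three items shared with the eczema scales can conceal children who got worse

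*Protocol*

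**What the plan says.** **Items and schedule.** Protocol Appendix D: "The following application site reactions will be evaluated at each visit based on the scale provided below". The items are burning, erosion, edema, pain, itching and dryness, each graded absent, mild, moderate or severe (0 to 3). The schematic in Protocol 5.0 places the scoring at Visits 1, 2 and 3.

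**Timing relative to dosing.**
- Visit 1 (Protocol 9.5.1): the reactions are scored within step 6. Drug is dispensed at step 11. Step 12 is the supervised application: "The first dose of study medication should be administered by the patient" or by a parent or guardian, depending on age. No site score is listed after it.
- Visit 2 (9.5.2, Day 14 ± 2): scored during treatment given "twice daily (morning and evening) for 28 days" (9.4.1). No dose hold is stated before this visit.
- Visit 3 (9.5.3, Day 29 ± 2): under 9.5, "subjects should not apply the study drug within 12 hours of Visit 3".

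**Summary.** SAP 7.3.7: "A frequency summary table comparing application site reaction for each cohort will be presented by visit". Shell T16.1.9.17 gives counts and percents per grade, by item, visit and cohort. It has no change from Visit 1, shift or worst post-baseline score. Listing L16.2.6.7 prints each patient's six scores at each visit.

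**Adverse events.** Protocol 9.7.1 counts events that worsen from baseline. The Synopsis (Safety Parameters) excludes signs and symptoms of atopic dermatitis unless they increase so far that dropping the patient from the study is judged to be in that patient's best interest.

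**The concern.** A score taken before any exposure cannot be a reaction to the drug. The Visit 1 column therefore records baseline skin status, yet it appears under a site-reaction title without being marked as pre-dose.

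Entry requires an EASI of at least 15 and an IGA of 3 or 4, so many children are likely to have itching, edema or erosion at that point. If the eczema responds, these scores fall for reasons unrelated to local tolerability. A table of separate visit frequencies adds improvements and deteriorations together and reports only the net result.

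At stake is the reading of local tolerability, which bears on the secondary objective covering the adverse event profile. A reader could take a falling column as evidence that the spray was well tolerated when some children had new or worse scores.

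**Working it through.** The documents give no expected rates, sample size or power for site reactions, so there is no figure to reproduce. The check has two parts.

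**1. Overlap with the eczema scales**

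| Appendix D item | Also in Protocol Appendix B? |
|---|---|
| Itching | Yes: the pruritus rating |
| Edema | Yes: within an EASI sign, whose zero grade is "No evidence of any induration/papulation/edema" |
| Erosion | Yes: within the excoriation grade descriptions |
| Burning | No |
| Pain | No |
| Dryness | No |

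Three of six overlap.

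**2. What visit frequencies leave undetermined**

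All counts below are assumed for illustration.

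*Present or absent.* Let n be the number of children, a the number with the item at Visit 1, b the number with it at Visit 3, and m the number of new cases. The visit counts fix only

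max(0, b − a) ≤ m ≤ min(n − a, b).

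With n = 10, a = 8, b = 4: max(0, −4) = 0 and min(2, 4) = 2. The table shows 80% falling to 40% whether new cases number 0, 1 or 2 (0% to 20%).

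*Four grades.* The number worsened is the count above the diagonal of the 4×4 table of Visit 1 grade by later grade. The plan's table fixes only the margins. The smallest and largest counts compatible with assumed margins (absent/mild/moderate/severe) are:

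| n | Visit 1 | Later visit | Worsened, min to max |
|---|---|---|---|
| 10 | 0/2/5/3 | 3/4/2/1 | 0 to 3 |
| 10 | 2/3/3/2 | 4/4/1/1 | 0 to 4 |
| 20 | 0/4/10/6 | 6/8/4/2 | 0 to 6 |
| 5 | 0/1/3/1 | 2/2/1/0 | 0 to 1 |
| 10 | 8/2/0/0 | 7/2/1/0 | 1 to 3 |
| 10 | 10/0/0/0 | 7/2/1/0 | exactly 3 |

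The first row can be checked by hand. Nobody is absent at Visit 1, so nobody can worsen into mild. The worsened must end as moderate (2 places) or severe (1 place), so the maximum is 2 + 1 = 3. It is reached if 2 mild become moderate and 1 moderate becomes severe; the other 4 moderate and 3 severe then fill the 3 absent and 4 mild places. The minimum is 0 if nobody moves up.

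In the second row, 2 absent become mild, 1 mild becomes moderate and 1 moderate becomes severe: 2 + 1 + 1 = 4. The remaining 2 + 2 + 2 = 6 fill 4 absent and 2 mild.

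The last row marks the limit of the problem. When an item is absent in everyone at Visit 1, the visit table gives the number worsened exactly.

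**The case against.** The strongest reply is that little is truly lost. SAP 7.3.7 lists all data by patient, and with 25 to 50 patients a reviewer can find every worsening in L16.2.6.7. Adverse events are collected by solicited and unsolicited means (Protocol 9.7), families record them in diaries (9.4.6), and Visit 2 asks about events since the previous visit. Site reactions are not an outcome measure in SAP section 6.

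Most of this stands, and it keeps the point small. It does not remove it. A listing is not a planned summary. The adverse event route is weakest for the three overlapping items, because of the Synopsis exclusion.

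A reader might also infer more than the documents support:

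- *That reactions are never scored during dosing.* Visit 2 is on treatment with no stated hold.
- *That the items are mostly eczema signs.* Three of six are. A fourth, dryness, counts only by assumption, and Protocol 7.4 names burning, itching and dryness as known topical corticosteroid reactions.
- *That immediate reactions are the expected ones, so a score after the supervised first dose is needed.* The documents say nothing about when a spray reaction would occur.
- *That the grid is deficient for omitting skin atrophy, striae or hypopigmentation.* Section 7.4 lists many reactions, among them "maceration of the skin, secondary infection, skin atrophy, striae and milia". Selecting a few for the grid is a preference, and the adverse event report and the Visit 3 physical examination can record them.
- *That the adverse event objective is biased.* It rests on tables T16.1.9.9 to T16.1.9.13, not on T16.1.9.17 alone.

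**Conclusion.** The point holds as one about tabulation. For itching, edema and erosion, the planned table can show clear improvement while an unknown number of children worsened: 0 to 3 or 0 to 4 of 10 in the assumed examples. The actual size depends on how many children have these items at Visit 1 and how the eczema responds, neither of which the documents give. The table can track disease improvement; nothing shows that it must. Items absent at Visit 1 are not affected.

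Two assumptions matter. The pre-dose status of the Visit 1 score is inferred from the step numbering and from dispensing only once eligibility is established. The Synopsis exclusion is assumed to be applied as written, although 9.7.1 is broader and an investigator could still report a worsening as a drug reaction.

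This is a low-cost improvement to a secondary safety summary. The primary HPA endpoint is not affected.

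**What to change.** In SAP 7.3.7 and shell T16.1.9.17:

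1. Label the Visit 1 column as the pre-dose baseline.
2. Add, by item and cohort, the number and percent of patients whose score exceeds their own Visit 1 score at Visit 2, at Visit 3 or early termination, and at the worst post-baseline assessment.
3. State the denominator: patients with a Visit 1 score and at least one score at the time point concerned.

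In the assumed examples, a range of 0 to 3 or 0 to 4 of 10 would become one known count.

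The cost is SAP wording and one added block in an existing table. The scores are already collected and listed, and the SAP already plans shift tables for laboratory data (7.3.3). No visit, procedure, CRF field or protocol amendment is needed. Protocol 10.1 has the SAP finalised before database lock, so the change should be made by then.
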